7.2 STATISTICAL ANALYSES

Primary objectives a-e:

Describe the patient population at the baseline (initiation of tofacitinib), using the data collected. For each continuous variables (age, BMI, age at diagnosis, duration of disease, laboratory measures), provide the mean, median, sd, 25%Q and 75%Q values. For categorical variables (sex, smoking status, extent of colonic involvement, disease severity, endoscopic findings), report the number of patients, and proportion. Report proportion of missing values if present.

Secondary objective - Assess the Real-world Effectiveness of Tofacitinib

Secondary objective a:

For each patient, define the "on treatment" as Yes/No based on the latest available dose (at each timepoint 8, 16, 24 and 52 weeks). Patients marked with "not on treatment" prior to timepoint will be regarded as discontinued.

Report the proportion of patients on treatment, not censored at each timepoint.

Secondary objectives b, c, d, e, g, n:

For each patient, define the fulfilment of the remission/response criteria as Yes/No based on the latest available data (at each timepoint 8, 16, 24 and 52 weeks).

Report the proportion of patients on fulfilling the response/remission criteria, not censored at each timepoint.

Secondary objective f:

Define the time of response for each patient as first ever data-entry that fulfils response criteria. Fit competing-risk time-to-event model to the data, with time-to-event defined as time from index until response (event) or discontinuation (competing event), or end of data collection (censoring event).

Assess the cumulative incidence as function of time for both types of events. Illustrate the Aalen-Johansen state probabilities of multistate model.

Secondary objective h:

Select only patients with baseline f-calprotectin above 250 mg/kg at baseline. For each subsequent f-calprotectin measure, define below 250 mg/kg as Yes/No variable. Additionally, estimate the absolute delta change per baseline value.

For each timepoint (week 8, 16, 24 and 52), report the proportion of patients on fulfilling the <250mg/kg criteria, and summary statistics (mean, median, sd, 25%Q and 75%Q) of delta change, among patients not censored at each timepoint.

Secondary objectives i, j, k, m, o:

Select only patients that were on remission/steroid free remission at the timepoints. For each patient, define the fulfilment of the remission/response criteria as Yes/No based on the latest available data (at each timepoint 16, 24 and 52 weeks). Report the proportion of patients on fulfilling the remission criteria, not censored at each timepoint.

Secondary objective l:

For each available Mayo score (full or partial), estimate the absolute delta change from baseline value. For each timepoint (week 8, 16, 24 and 52), report the summary statistics (mean, median, sd, 25%Q and 75%Q) of delta change, among patients not censored at each timepoint.

Secondary objective p:

Perform analyses described in secondary objective b and c, stratified by the extent of colonic involvement

Secondary objective q:

For each patient, define the corticosteroid tapering as Yes/No based on the latest available data (at each timepoint 8, 16, 24 and 52 weeks). Additionally, define the tapering rates and doses based on latest available data.

For each timepoint (week 8, 16, 24 and 52), report the proportion of patients that had corticosteroid tapered, among patients not censored at each timepoint. Additionally,

report summary statistics (mean, median, sd, 25%Q and 75%Q) of tapering rates and doses among patients that had corticosteroids tapered.

Secondary objectives r and s:

For each patient, define the fulfilment of the improvement criteria as Yes/No based on the latest available data (at each timepoint 8, 16, 24 and 52 weeks). Additionally, estimate the absolute delta change per baseline value

Report the proportion of patients on fulfilling the response/remission criteria, report the summary statistics (mean, median, sd, 25%Q and 75%Q) of delta change, among patients not censored at each timepoint.

Secondary objectives t-z:

For each subsequent laboratory measure, define "normal-level" as Yes/No variable. Additionally, estimate the absolute delta change per baseline value. For each timepoint (week 8, 16, 24 and 52), report the proportion of patients on fulfilling the "normal-level" criteria and summary statistics (mean, median, sd, 25%Q and 75%Q) of delta change, among patients not censored at each timepoint.

Secondary objective aa:

Report the proportion of patients that received extended induction

Secondary objective bb:

For each subsequent visit, define the higher (10mg) dosing as Yes/No variable. For each timepoint (week 8, 16, 24 and 52), report the proportion of patients, among patients not censored at each timepoint.

Secondary objective cc:

Create composite endpoint of drug discontinuation, colectomy or UC-hospitalization, with time of the event as earliest of the aforementioned. Analyse time to event using Kaplan-Meier fit, where time to event is defined as time from index until composite endpoint (event) or time of data collection (censoring event).

Plot the Kaplan-Meier fit with the 95% CI and report the median survival if reached.

Secondary objective - Assess Treatment Lines Prior to Tofacitinib Treatment

Secondary objective a:

Summarize and tabulate types of previous UC treatments. Report N and proportion of patients that had corresponding treatment recorded.

Report the summary statistics (mean, median, sd, 25%Q and 75%Q) of number of treatments prior to tofacitinib if feasible.

NA

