#### 7.3. Secondary objectives

#### 7.3.1. To Assess the Real-world Effectiveness of Tofacitinib.

- a. Proportion of patients who are taking to facitinib at week 8, 16, 24 and 52.
- b. To assess rates of clinical remission defined by a full or partial Mayo score at week 8, 16, 24 and 52.
- c. To assess rates of clinical response defined by a full or partial Mayo score at week 8, 16, 24 and 52.
- d. Proportion of patients in steroid-free clinical remission at weeks 8, 16, 24, and 52 as defined by full or partial Mayo who did not require any corticosteroid treatment during the period ≥4 weeks prior to the visit (for all patients and for those treated with corticosteroids at baseline).
- e. Proportion of patients reaching clinical response as defined by full or partial Mayo score at week 8, 16, 24 and 52.

- f. Time to response as assessed by a decrease as defined by full or partial Mayo score.
- g. Proportion of responders defined by a f-calpro reduction of  $\geq 50\%$ ,  $\geq 75\%$  or  $\geq 90\%$  at week 8, 16, 24 and 52 compared to baseline.
- h. Proportion of patients reaching f-calpro below 250 mg/kg at week 8, 16, 24 and 52 of those that had f-calprotectin above 250 mg/kg at baseline and change from baseline in f-calpro at week 8, 16, 24 and 52.
- i. Proportion of patients in sustained remission (pMayo and full Mayo score) from week 8 to week 16, 24 and 52.
- j. Proportion of patients in sustained remission (pMayo and full Mayo score) from week 16 to week 24 and 52.
- k. Proportion of patients in sustained steroid free remission (pMayo and full Mayo score) at week 16 to 24 and 52 (for all patients and for those treated with corticosteroids at baseline).
- 1. Change in partial and full Mayo score at weeks 8/16/24/52.
- m. Proportion of patients in sustained endoscopic remission (sub score = 0), mucosal healing (sub score 0-1) or endoscopic response (sub score reduction from baseline of ≥1) from week 8 to week 16, 24 and 52.
- n. Proportion of patients in physician assessed histological remission determined as inactive disease, or normal histology, and change from baseline in histology assessment (0= normal histology, 1= inactive disease and 2 = active disease) at week 8/16/24/52.

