#### 8.7. Data Analysis

Detailed methodology for summary and statistical analyses of data collected in this study will be documented in a SAP, which will be dated, filed, and maintained by the sponsor. The SAP may modify the plans outlined in the protocol; any major modifications of primary endpoint definitions or their analyses would be reflected in a protocol amendment.

All analysis will be performed by Medaffcon. In short, patients will be described at baseline using appropriate summary statistics.

All analyses are descriptive of nature, and descriptive statistics and/or illustrations will be reported.

Persistence of treatment will be assessed using time-to-event models (namely Kaplan-Meier fit and/or Cox proportional hazards model). Changes in treatment outcomes (vs. baseline) will be assessed using repeated measures longitudinal models. Baseline data may be used as covariates in the models where feasible and appropriate.

All p-values are descriptive in nature, and there are no *a priori* hypotheses to be tested. P-values lower than 0.05 will be considered statistically significant. All statistical tests will be considered hypothesis generating, and any significant results should be validated later.

Statistical interpretation of the results will be validated by Medaffcon statisticians/Data Scientists with relevant degree.

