#### 8.9. Limitations of the Research Methods

The main strength of this study is the nation- and patient-wide coverage of the cohort. The study is expected to include all 21 health care districts in Finland. The data is also versatile as it is derived from the patient information systems in the hospital districts.

The main limitation of the study are its' retrospective nature and the expected number of observations (approximately 100-150 patients). Therefore, some sub-group or stratified analyses are not necessarily possible. It is also likely that the data is partially incomplete because of the variation between hospitals. All variables or sum variable components are not necessarily available from different electronical health records. To a citinib has been used in Finland for a rather short time so data for all endpoints at all timepoints may not be calculated/available. As in the registry studies in general the primary data source (hospital electronic health record [EHR]) in this study may be prone to potential human errors. Data is subject to gaps and human errors made by physicians entering data into the system.

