7 STATISTICAL METHODOLOGY AND STATISTICAL ANALYSES

7.1 STATISTICAL METHODS

General:

Means, medians, and standard deviations, and 25% and 75% quartiles will be provided for continuous variables when performing descriptive analysis of continuous data. Numbers and percentages will be provided for dichotomous and polychotomous variables when performing descriptive analysis of categorical data.

Serial measures collected will be handled by "carry forward imputation", i.e. the latest value will be assumed unchanged until otherwise proven. Thus for each timepoint, the latest available measure will be used. Patients will be censored from the study post the last available contact/data entry. Missing values will not be imputed.

An unadjusted Kaplan Meier curve will be drawn to illustrate time-to-event and to estimate medians for time-to-event outcomes.

All data analysis will be executed using R, a language and environment for statistical computing and graphics, version 4.0.3 or later in Rstudio environment.

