8 TABLE SHELLS

Table 2: Table shell for patient characteristics for primary objective

				n	missing
Variable	categories	mean (sd)	Median (25Q-75Q)	(%)	%
age				-	
sex	male	-	-		
	female	-	-		
weight				-	
height				-	
(BMI)				-	
smoking	current	-	-		
	ex-smoker	-	-		
	non-smoker	-	-		
age at UC diagnosis				-	
duration of UC				-	
Montreal classification	E1	-	-		
	E2	-	-		
	E3	-	-		
Mayo-score				-	
F-calpro				-	
P-CRP				-	
B-thromb				-	
P-alb				-	
B-leuk				-	
B-ly				-	
B-neutr				-	
B-hb				-	
Endoscopic findings	yes	-	-		
	no	-	-		

Table 3: Table shell for outcome objectives

Objective	Outcome	Week 8	Week 16	week 24	week 52
1	N patients	N	N	N	N
P1 - a	Proportion of patients on treatment	n (%)	n (%)	n (%)	n (%)
P1 - b	Proportion of patients with clinical remission (full Mayo)	n (%)	n (%)	n (%)	n (%)
P1 - b	Proportion of patients with clinical remission (partial Mayo)	n (%)	n (%)	n (%)	n (%)
P1 - c	Proportion of patients with clinical response (partial Mayo)	n (%)	n (%)	n (%)	n (%)
P1 - c	Proportion of patients with clinical response (full Mayo)	n (%)	n (%)	n (%)	n (%)
P1 - d	Proportion of patients with steroid free clinical remission	n (%)	n (%)	n (%)	n (%)
P1 - g	Proportion of patients with f-calpro reduction ≥50%	n (%)	n (%)	n (%)	n (%)
P1 - g	Proportion of patients with f-calpro reduction ≥75%	n (%)	n (%)	n (%)	n (%)
P1 - g	Proportion of patients with f-calpro reduction ≥90%	n (%)	n (%)	n (%)	n (%)
P1 - h	Proportion of patients reaching f-calpro below 250 mg/kg, of those that had f-calprotectin above 250 mg/kg at baseline	n (%)	n (%)	n (%)	n (%)
P1 - h	Change in f-calpro, among patients with f-calprotectin above 250 mg/kg at baseline	Δ -from baseline (mean ± sd)	Δ-from baseline (mean ± sd)	Δ-from baseline (mean ± sd)	Δ-from baseline (mean ± sd)

Objective	Outcome	Week 8	Week 16	week 24	week 52
P1 - i	Proportion of patients in sustained remission (pMayo) from week 8	-	n (%)	n (%)	n (%)
P1 - i	Proportion of patients in sustained remission (full Mayo score) from week 8	-	n (%)	n (%)	n (%)
P1 - j	Proportion of patients in sustained remission (pMayo) from week 16	-	-	n (%)	n (%)
P1 - j	Proportion of patients in sustained remission (full Mayo score) from week 16	-	-	n (%)	n (%)
P1 - k	Proportion of patients in sustained steroid free remission (pMayo) from week 16	-	-	n (%)	n (%)
P1 - k	Proportion of patients in sustained steroid free remission (full Mayo score) from week 16	-	-	n (%)	n (%)

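### The SAP has no stand-alone time-to-discontinuation analysis, leaves the denominator of the on-treatment proportion open, and states censoring for f and cc in terms that conflict with its own general rule

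*SAP*

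**What the plan says.** **Persistence.** Protocol 8.7: "Persistence of treatment will be assessed using time-to-event models (namely Kaplan-Meier fit and/or Cox proportional hazards model"). Protocol 7.3.1.a asks for the proportion of patients taking the drug at four timepoints. SAP 7.2, secondary objective a, sets on-treatment status "as Yes/No based on the latest available dose (at each timepoint 8, 16, 24 and 52 weeks"), regards anyone marked as not on treatment before the timepoint as discontinued, and then instructs: "Report the proportion of patients on treatment, not censored at each timepoint". The Table 3 row P1-a, "Proportion of patients on treatment", holds n (%) only. The first row of that table gives N by week without defining it.

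**Latitude.** Protocol 8.7 also says: "The SAP may modify the plans outlined in the protocol". It requires an amendment only for major changes to primary endpoint definitions or their analyses.

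**Censoring.** SAP 7.1, under its general methods: "Patients will be censored from the study post the last available contact/data entry". Table 1 uses the date of death or loss to follow-up to define the end of follow-up. In SAP 7.2, however, objective f gives the end of data collection as its censoring event, and objective cc gives the time of data collection. Neither mentions last contact, loss or death.

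**The concern.** Persistence and event-free survival are the study's durability results. Three things are unsettled.

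- The SAP never estimates the probability of still being on drug over time. Composite cc mixes stopping with colectomy and UC hospitalization. In f a stop counts only if it comes before response. The SAP annotates other changes to the protocol objectives (b and c, c and e, q) but has no note here, so the omission does not look deliberate.
- Being not censored at a timepoint can mean that every patient needs follow-up to that week, or that a known stopper stays in the denominator wherever the record ends. Two competent analysts could report different figures.
- A programmer normally codes the objective-specific text. Under the wording in f and cc, a patient lost at month 4 stays at risk and event-free until data collection.

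Partial follow-up will be common. Protocol 8.9 notes the drug's short use in Finland, "so data for all endpoints at all timepoints may not be calculated/available".

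**Working it through.** The documents give no persistence, loss or event rate, so there is no stated figure to reproduce. All rates below are assumptions. Time is in years of 52 weeks unless stated, with constant hazards.

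**1. Follow-up available.** Assume uniform starts from 1 March 2019 (reimbursement) and a cut at 1 December 2021 (start of data collection), 143.7 weeks later. With at least 8 weeks since start, potential follow-up runs from 8 to 143.7 weeks. The share that cannot reach week 52 is (52 − 8)/(143.7 − 8) = 44/135.7 = 32%.

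**2. Objective a, denominator, no loss.** Assume true persistence of 60%, so the weekly hazard is −ln(0.60)/52 = 0.00982.
- Share with follow-up beyond week 52: 91.7/135.7 = 0.676.
- Of all patients, on drug and followed: 0.60 × 0.676 = 0.405. Stopped and followed: 0.40 × 0.676 = 0.270.
- Stopped, with potential follow-up shorter than 52 weeks: [44 − (e^(−8×0.00982) − 0.60)/0.00982]/135.7 = (44 − 33.0)/135.7 = 0.081.
- Stoppers without 52 weeks dropped: 0.405/(0.405 + 0.270) = 60%.
- Stoppers kept: 0.405/(0.405 + 0.270 + 0.081) = 53.6%. Late starters can then enter the denominator only by stopping. Spreading the data mining uniformly to 30 May 2022 gives 55.2% (simulated).

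**3. Objective a with loss, stoppers dropped.** Let λ = −ln(0.60) = 0.511, μ = −ln(1 − p) for yearly loss p, and let loss be k times as likely after stopping. Then:
- on drug and followed = 0.60 × (1 − p)
- stopped and followed = λ e^(−kμ) × (1 − e^(−(λ+μ−kμ)))/(λ + μ − kμ)

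| k | p = 5% | p = 10% |
|---|---|---|
| 1 | 60% | 60% |
| 3 | 0.570/(0.570 + 0.360) = 61.3% | 0.540/(0.540 + 0.322) = 62.7% |
| 1/3 | 0.570/(0.570 + 0.387) = 59.6% | 0.540/(0.540 + 0.374) = 59.1% |

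In simulations with N = 125 and exactly dated stops, Kaplan-Meier censored at last contact averaged 59.8 to 60.2% in every scenario. Its standard error was 4.5 to 5.1 points, against 5.0 to 6.0 for the crude figure. If stops are known only at contacts 8 or 12 weeks apart and dated there, Kaplan-Meier itself reads 61 to 63%.

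**4. Objective cc coded literally.** If lost patients stay at risk to data collection, the curve estimates S(t) = 1 − λ/(λ+μ) × (1 − e^(−(λ+μ)t)). For a true 52-week value of 50%, λ = 0.693.

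| Yearly loss | S at 52 weeks | Median (true 52 weeks) |
|---|---|---|
| 0 | 50.0% | 52.0 |
| 5% | 1 − 0.931 × 0.525 = 51.1% | 53.8 |
| 10% | 1 − 0.868 × 0.550 = 52.3% | 55.9 |
| 20% | 1 − 0.756 × 0.600 = 54.6% | 61.4 |

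For a true value of 60% the readings are 60.9, 61.9 and 63.8%.

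**5. Objective f coded literally.** Each cumulative incidence is h_k/(h1+h2+μ) × (1 − e^(−(h1+h2+μ))). Assume true 52-week values of 50% response and 30% discontinuation, so h1 + h2 = −ln(0.20) = 1.609, split 5:3. The readings are 49.1/29.4, 48.1/28.9 and 46.1/27.7% at 5, 10 and 20% loss.

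**6. Scale.** The 95% half-width for a proportion near 50% is 1.96 × √(0.25/N), which is 9.8 points at N = 100 and 8.0 at N = 150.

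**The case against.** **The SAP delivers what objective a asks for.** Protocol 7.3.1.a wants a proportion. Only cc is marked for time-to-event analysis, it includes discontinuation, and it already has a Kaplan-Meier curve with confidence interval and median. A reader might infer that the SAP breaches the protocol. The documents do not support that, because 8.7 lets the SAP change plans and this is not a primary endpoint. What remains is that cc does not isolate persistence, and that a method the protocol names is absent without comment.

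**SAP 7.1 already holds the censoring rule.** It is a general statement, and the phrase about patients not censored in 7.2 takes its meaning from it. A reader might infer that the SAP forgot censoring at last contact. It did not. The figures in steps 4 and 5 arise only if 7.1 is set aside. This is a conflict between general and specific text, and it still needs one answer.

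**The crude proportion need not be biased.** A reader might infer that it overstates persistence. With stoppers lacking follow-up dropped, it is unbiased when loss is unrelated to stopping, and the documents give no ground for either direction. This stands. The ambiguity in step 2 needs no loss at all.

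**Restarts.** Taking the first not-on-treatment entry as the event might seem to clash with the latest-dose rule. It does not, because the SAP already regards such patients as discontinued.

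**Conclusion.** The point holds as an unexplained departure plus two specification gaps. No stand-alone time-to-discontinuation analysis is specified although protocol 8.7 names one. The denominator of objective a is open, which is worth about 6 points at week 52 under an assumed 60% persistence, uniform entry and no loss. The censoring text in f and cc conflicts with SAP 7.1 and Table 1. Read literally, that text moves 52-week event-free survival by about 1 to 5 points at an assumed 5 to 20% yearly loss, always upward, and by nothing without loss.

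These shifts lie within the sampling error expected at 100 to 150 patients, and the results are secondary and descriptive. The reason to act is that the SAP as written permits different answers from the same data. Kaplan-Meier uses partial follow-up and avoids the denominator choice, but it does not remove bias from stops recorded late.

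**What to change.** 1. **Objective a and row P1-a.** Keep the n/N that protocol 7.3.1.a asks for. Restrict it to patients with follow-up through the timepoint, and define the N row of Table 3 that way for this outcome. Beside it, add a Kaplan-Meier analysis of time to the first entry recording that the patient is not on treatment, with 95% CI at weeks 8, 16, 24 and 52 and the median if reached. State whether a stop is dated at the charted stop date or at the contact that recorded it.
2. **Objectives a, f and cc.** Reconcile the text with SAP 7.1 and Table 1. State that patients are censored at the earliest of last contact or data entry, loss to follow-up, and data collection. State explicitly how death is handled in each analysis. Leave the cc composite unchanged.

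The cost is a few sentences of SAP text and one added table row. It also needs a check that stop and last-contact dates can be derived from dated eDMT entries, since Table 1 lists no separate field for either, and that death can be told apart from loss, since Table 1 puts them in one row. The export limit on groups under 5 patients (protocol 8.6) applies to the added curve as it does to the planned cc curve. Event-free survival may come out slightly less favourable than under the literal reading.

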#### 5. MILESTONES

Milestone	Planned date
Start of data collection	01 December 2021
End of data collection	30 May 2022
Final study report	01 May 2023

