#### 8.2.2. Exclusion Criteria

Patients meeting any of the following criteria will not be included in the study:

- 1. Age <18 years at the start of tofacitinib use.
- 2. Use of tofacitinib before reimbursement (01 Mar 2019).
- 3. < 8 weeks of treatment with tofacitinib at the start of data mining.
- 4. History of panproctocolectomy, IPAA or ileostomy.

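### Week 52 in SAP Table 3 describes a different, earlier-starting set of patients than week 8, and no planned display of the on-drug and remission proportions holds the cohort fixed

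*SAP*

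**What the plan says.** SAP 7.2 evaluates treatment status, remission and response "at each timepoint 8, 16, 24 and 52 weeks". For objective a the instruction is "Report the proportion of patients on treatment, not censored at each timepoint". Objectives b-e, g and n carry the same restriction, as do the sustained-outcome objectives (i, j, k, m, o). For h, l, q, r-s, t-z and bb the wording is "among patients not censored at each timepoint". SAP 7.1 defines the censoring: "Patients will be censored from the study post the last available contact/data entry".

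Entry is staggered. Protocol 8.2.2 excludes use before reimbursement on 1 March 2019 and also excludes "< 8 weeks of treatment with tofacitinib at the start of data mining". Protocol section 5 plans data collection from "01 December 2021" to 30 May 2022. A note under the study timeline in protocol 8.2 says that dates may move with the permit process.

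SAP Table 3 sets weeks 8, 16, 24 and 52 side by side, with a row for N in each column. Protocol 8.9 concedes that "data for all endpoints at all timepoints may not be calculated/available" because the drug has been in use for only a short time.

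**The concern.** By calendar date, every included patient can reach week 8. A patient who started in summer 2021 cannot reach week 52 on either planned collection date. The late-starting part of the week-8 column is therefore missing from the week-52 column.

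The table's layout invites reading from left to right as the course of treatment. If early and late starters differ in prognosis or prior treatment, a rise or fall between columns can appear although no patient's status has changed. For the proportions on drug, in remission and in steroid-free remission, no planned display keeps the same patients in view across the four weeks.

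**Working it through.** The plan gives no expected share reaching week 52, so there is no figure to reproduce. What follows is date arithmetic on the plan's own dates.

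**Inputs**
- Earliest start: 1 March 2019 (protocol 8.2.2).
- Latest start: 1 December 2021 minus 56 days = 6 October 2021 (protocol 8.2.2 and 5).
- Entry window: W = 950 days.
- Follow-up cut: 1 December 2021 at the earliest, 30 May 2022 at the latest (protocol 5).
- Planned size: 100-150 patients (protocol 8.5).
- Uptake over time: not given. Three assumed shapes are used: constant, rising linearly from zero, and falling linearly to zero.

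**Formula.** Let f = (cut − 364 days − 1 March 2019) / W. The share able to reach week 52 is f under constant uptake, f² under rising uptake, and 1 − (1 − f)² under falling uptake.

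| Follow-up cut | Latest start for week 52 | f | Constant | Rising | Falling |
|---|---|---|---|---|---|
| 1 Dec 2021 | 2 Dec 2020 | 642/950 = 0.676 | 68% | 46% | 89% |
| 30 May 2022 | 31 May 2021 | 822/950 = 0.865 | 87% | 75% | 98% |

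Of 100-150 patients, 46-69 could reach week 52 in the lowest case (rising uptake, December cut), 87-130 under constant uptake with the May cut, and 98-147 in the highest case (falling uptake, May cut).

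If the 8-week rule were instead applied at 30 May 2022, W would be 1,130 days. The shares would be 822/1130 = 73% (constant), 53% (rising) and 93% (falling).

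**Weeks 16 and 24.** With the 1 December 2021 cut, week 16 is reachable for 94% (constant) or 89% (rising), and week 24 for 88% or 78%. With entry closing on 6 October 2021 and a 30 May 2022 cut, both are 100%. The last starter reaches week 16 on 26 January 2022 (6 October + 112 days) and week 24 on 23 March 2022 (6 October + 168 days). Calendar loss in these columns thus arises only if follow-up is cut before those dates.

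**Possible shift, for illustration only.** If early and late starters have different but constant remission rates, then week-52 column − week-8 column = (1 − share reaching week 52) × (early rate − late rate). The difference in rates is an assumption.

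| Share reaching week 52 | 10-point difference | 20-point difference |
|---|---|---|
| 46% | 5.4 points | 10.9 points |
| 68% | 3.2 | 6.5 |
| 87% | 1.4 | 2.7 |
| 98% | 0.2 | 0.4 |

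With no difference, the shift is zero.

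**Loss other than by calendar.** SAP 7.1 censors at last contact, so a patient who started in 2019 and was last seen at week 30 also leaves the week-52 column. The documents give no rate for this loss, and the table above does not include it.

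**The case against.** The strongest reply is that the study is descriptive, has no hypotheses, and plans no test between weeks. Under purely administrative censoring, each column correctly describes the patients in it. The N row shows the denominator changing, and protocol 8.9 discloses incomplete timepoints. Objective f (competing risks) and objective cc (Kaplan-Meier) follow the cohort from the index date and handle censoring. Objectives i, j, k, m and o follow patients forward from an anchor week. Objectives h, l and r-z include change from baseline, which removes differences in baseline level.

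Much of this stands, and it rules out several stronger inferences that a reader might draw:
- **That the week-52 figures are wrong.** They are not; the difficulty lies in comparing them with earlier columns.
- **That the documents fix the share at 46-87%.** That range needs constant to rising uptake and the planned dates. Falling uptake gives 89-98%.
- **That all four columns necessarily differ.** With follow-up to 30 May 2022 on the planned entry dates, calendar loss touches only week 52.
- **That a bias of known size is present.** Nothing in the documents shows that early and late starters differ.

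The mitigation is still partial. The N row shows how many patients left, not which ones. Objective f gives time to first response, and cc gives a composite; neither gives the proportion on drug, in remission or in steroid-free remission at each week. The sustained-outcome objectives select on outcome and still drop censored patients. Change from baseline does not help if early and late starters change by different amounts.

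Protocol 8.7 calls for time-to-event models for persistence and repeated-measures models for change. The SAP uses neither for objectives a and l. Protocol 8.7 lets the SAP modify the protocol's plans, so this is not a breach, but it leaves the gap open.

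**Conclusion.** The point holds for comparisons of week 52 with earlier weeks. It extends to weeks 16 and 24 only if follow-up is cut early in the collection period or the 8-week rule is applied close to the cut. By calendar date alone, about 46-87% could reach week 52 under constant to rising uptake, and up to about 98% under falling uptake, on planned dates that may move. Censoring at last contact can lower these shares by an amount that the documents do not give.

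The size of any distortion cannot be derived from the documents; the illustrative shifts rest entirely on assumed differences between early and late starters. No planned number is invalid in itself. The change is worth making because the main effectiveness table invites a time-course reading that its denominators do not support, and the remedy is cheap.

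**What to change.** Keep the all-available columns and add the following.

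1. **A fixed-cohort panel in Table 3** for objectives a, b, c, d and l, limited to patients whose tofacitinib start is at least 52 weeks before their own data-collection date. Membership depends only on dates, not on outcome.
2. **One fixed denominator in all four columns of the panel.** A date filter alone does not achieve this, because censoring at last contact would still remove patients. Show those whose last contact came before a timepoint as a separate no-data count rather than dropping them. For objective l, show that count beside the summary statistics.
3. **Kaplan-Meier time on drug in all patients** for objective a, in line with protocol 8.7 on persistence. This keeps all 100-150 patients and counts a recorded discontinuation at its date.
4. **One line comparing baseline Mayo score and number of prior treatments** between panel patients and the rest. These variables are already collected.

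The programming cost is a date filter, one table panel and one curve; objective cc already needs the data-collection date. The panel would hold about 46-69 patients in the lowest case worked out above and 98-147 in the highest. For a proportion near 50%, the 95% half-width, 1.96 × √(0.25/n), is about 14 points at n = 46 and 9 points at n = 130, against 8-10 points for 150-100 patients. Cells below 5 cannot be exported (protocol 8.6), so some panel entries may be suppressed.
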